7.5 Statistical Analyses for Safety

The safety analyses will be performed using the safety population. The safety parameters will include incidence of AEs, change from baseline in vital signs and laboratory (hematology/chemistry) assessments, and ECG. Safety endpoints will be summarized using descriptive statistics and/or shift tables, as applicable.

Treatment-emergent AEs are defined as any AE with the onset that is after the first dose of study drug. Events where the onset date is the same as the study drug start date are assumed to be treatment-emergent.

An overview of AEs will be presented consisting of the number and percentage of subjects experiencing at least one event for each of [REDACTED] AE categories:

- Any treatment-emergent AE
- Any treatment-emergent AE related to study treatment according to the investigator
 - [REDACTED]
 - [REDACTED]
 - [REDACTED]
 - [REDACTED]
 - [REDACTED]
- Any PDSOT AEs
- All deaths

SAEs (including deaths) will be summarized by SOC and PT and in listing format.

PDSOT AEs will be identified in the SAP and summarized by PT.

Statistical Analyses for Immunogenicity and Hypersensitivity

Immunogenicity results, manifested as the binding antibodies and neutralizing antibodies, will be summarized in a table for each sampling timepoint. [REDACTED]

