Investigational Plan:	This is a 270-day, double-blind, randomized, placebo-controlled, Phase 2 study to assess the safety and efficacy of OnabotA X in adult subjects (\geq 18 years old) with moderate to severe GL. Eligible subjects will be randomized in a 2:2:2:1 ratio to receive OnabotA X [REDACTED] [REDACTED] or [REDACTED] placebo [REDACTED]. Randomization will be stratified at each investigator site by the investigator-assessed baseline severity of GL at maximum contraction using the AGLSS.

Key Eligibility Criteria:	To be eligible for enrollment, at baseline subjects must have AGLSS scores of moderate or severe GL at maximum contraction (also called frown or furrow) by investigator and subject assessments. The investigator and subject scores must be the same.
Study Drug and Duration of Treatment:	On Day 1, eligible subjects will receive a single, double-blind treatment of OnabotA X [REDACTED] or [REDACTED] placebo. Study drug will be administered as [REDACTED] intramuscular (IM) injections into the corrugator and procerus muscles.
Date of Protocol Synopsis:	07 February 2022

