2.2 Benefits and Risks to Subjects

OnabotulinumtoxinA is the active drug substance in BOTOX/BOTOX Cosmetic and in OnabotA X; therefore, safety data from prior studies of BOTOX are relevant to the benefit/risk assessment for this first-in-human study of OnabotA X.

The clinical efficacy and safety profile of BOTOX has also been demonstrated in multiple Allergan- and non-Allergan-sponsored clinical trials across several indications, with favorable benefit/risk profiles. In general, adverse reactions occur within the first few days following injection of BOTOX, and while generally transient, may have a duration of several months or, in rare cases, longer.

In a meta-analysis conducted by Brin et al, the most frequently reported adverse events (AEs) among subjects treated for GL with BOTOX [REDACTED] were headache, nasopharyngitis, eyelid sensory disorder, eyelid ptosis, injection site pain, and nausea.⁹ All of these events were mild or moderate in severity, and the incidence decreased with increasing number of treatment cycles.

More detailed information about the known and expected benefits and risks and reasonably expected AEs of OnabotA X may be found in the Investigator's Brochure and the subject's informed consent form (ICF).

For further details, please see findings from completed studies, including safety data in the current OnabotA X Investigator's Brochure.

Considering the coronavirus disease – 2019 (COVID-19) pandemic, the benefit and risk to subjects participating in this study have been re-evaluated. Based on the limited information to date, no additional risk to study subjects is anticipated with the use of OnabotA X.

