Important Medical Event Requiring Medical or Surgical Intervention to Prevent Serious Outcome	An important medical event that may not be immediately life-threatening or result in death or hospitalization, but based on medical judgment, may jeopardize the subject and may require medical or surgical intervention to prevent any of the outcomes listed above (i.e., death of subject, life threatening, hospitalization, prolongation of hospitalization, congenital anomaly, or persistent or significant disability/incapacity). Additionally, any elective or spontaneous abortion or stillbirth is considered an important medical event along with any suspected transmission of an infectious agent via a medicinal product if no other serious criterion is applicable. Examples of such events include allergic bronchospasm requiring intensive treatment in an emergency room or at home, blood dyscrasias or convulsions that do not result in inpatient hospitalization, or the development of drug dependency or drug abuse.

All AEs reported from the time of study drug administration will be collected for at least 30 days or until the last follow-up visit, whichever is longer, whether solicited or spontaneously reported by the subject.

In addition, study procedure-related serious and nonserious AEs will be collected from the time the subject signs the study-specific informed consent.

AbbVie will be responsible for SUSAR reporting for the IMP in accordance with global and local requirements.

Possible Distant Spread of Toxin

Possible distant spread of toxin (PDSOT) is defined as a possible pharmacologic effect of botulinum toxin at sites noncontiguous and distant from the site of injection. Utilizing a standardized methodology to assess for PDSOT, Medical Dictionary for Regulatory Activities (MedDRA) preferred terms (PTs) that may be associated with botulinum toxin effects have been prospectively identified (see the statistical analysis plan [SAP] for a complete list of these PTs). AEs reporting any of these terms will be medically reviewed on a regular basis throughout the study and will be summarized in the clinical study report.

Adverse Event Severity and Relationship to Study Drug

The investigators will rate the severity of each AE as mild, moderate, or severe.

The investigator will use the following definitions to rate the severity of each AE:

Mild	The AE is transient and easily tolerated by the subject.

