10.2.1 Treatment-Emergent Adverse Events

All treatment-emergent AEs will be summarized overall, as well as by primary MedDRA SOC and Preferred Term.

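### No readable adverse event table is by time of onset, so full-study percentages can dilute an early drug effect on common complaints after the single Day 1 injection

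*Protocol*

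**What the plan says.** - **Dosing and length.** The Protocol synopsis says "This is a 270-day, double-blind, randomized, placebo-controlled, Phase 2 study". On Day 1 "eligible subjects will receive a single, double-blind treatment of OnabotA X" or placebo.
- **Definition.** Protocol 7.5: "Treatment-emergent AEs are defined as any AE with the onset that is after the first dose of study drug". No end to the window is given.
- **Collection.** Protocol 6.1 says that events from study drug administration onward "will be collected for at least 30 days or until the last follow-up visit, whichever is longer".
- **Tables.** SAP 10.2.1: "All treatment-emergent AEs will be summarized overall, as well as by primary MedDRA SOC and Preferred Term". SAP 10.2 presents events overall and by treatment group. SAP 10.2.2 counts subjects with at least one event, and SAP 10.2.3 adds tables by maximum severity. No readable table is by time of onset.
- **Expected timing.** Protocol 2.2: "In general, adverse reactions occur within the first few days following injection of BOTOX". The same sentence adds that reactions "may have a duration of several months or, in rare cases, longer". The most frequent events in the BOTOX meta-analysis that it cites "were headache, nasopharyngitis, eyelid sensory disorder, eyelid ptosis, injection site pain, and nausea".
- **Redactions.** Five overview categories in Protocol 7.5 and the text after the first sentence of SAP 10.2.3 are blacked out, as is the timing of the interim analyses.

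**The concern.** The window of the main safety tables does not match the period in which the protocol expects reactions to begin. Headache, nasopharyngitis and nausea also occur without treatment. Over nine months such events accumulate in every arm. A subject counts once per preferred term, so someone with a drug-related headache in week 1 looks the same as someone with an unrelated headache in month 7. This narrows the difference between arms and widens its standard error, and placebo has only about 40 subjects.

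Safety is a primary objective (Protocol 3.1). Under SAP 12.1 the data monitoring committee reviews interim safety and efficacy data to recommend a Phase 3 dose. If the tables by dose are a weak display of early reactions, part of the evidence for that recommendation is weaker than the data allow.

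**Working it through.** **The plan's own figure.** The documents give no adverse event rate, precision or power to reproduce. Safety is descriptive, and the sample size statement in Protocol 7.8 concerns efficacy only.

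**Inputs from the documents**
- Arm sizes: about 280 subjects at 2:2:2:1, so 280 × 2/7 = 80 per dose and 280 × 1/7 = 40 on placebo (Protocol 4.1).
- Full window: 270 days, or nine 30-day periods. This end is inferred from the definition, the collection rule and the study length together; no single sentence states it.
- Short window for comparison: 30 days, the minimum collection period in Protocol 6.1.

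**Assumptions**
- Background incidence *b* of one complaint per 30 days, constant over time: 1% to 8%, and 0.05% for a ptosis-like event.
- Early excess risk *e* from the drug, all within the first 30 days: 10%, and 5% for the ptosis-like event.
- No dropout.

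**Formulas**, with *k* = 1 for 30 days and *k* = 9 for 270 days:
- placebo: p0 = 1 − (1 − b)^k
- active: p1 = 1 − (1 − p0)(1 − e)
- SE = √[p1(1 − p1)/80 + p0(1 − p0)/40]
- contrast = (p1 − p0)/SE

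The contrast serves only as a signal-to-noise index, because the plan tests no adverse event.

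**Worked case, b = 5%, e = 10%**
- 30 days: p0 = 0.050; p1 = 1 − 0.95 × 0.90 = 0.145; difference 0.095; SE = √(0.145 × 0.855/80 + 0.050 × 0.950/40) = 0.052; contrast 1.8.
- 270 days: p0 = 1 − 0.95^9 = 0.370; p1 = 1 − 0.630 × 0.90 = 0.433; difference 0.063; SE = 0.094; contrast 0.7.

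**Range**

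| b per 30 days | e | 30 days: active v placebo | contrast | 270 days: active v placebo | contrast |
|---|---|---|---|---|---|
| 1% | 10% | 10.9% v 1.0% | 2.6 | 17.8% v 8.6% | 1.5 |
| 3% | 10% | 12.7% v 3.0% | 2.1 | 31.6% v 24.0% | 0.9 |
| 5% | 10% | 14.5% v 5.0% | 1.8 | 43.3% v 37.0% | 0.7 |
| 8% | 10% | 17.2% v 8.0% | 1.5 | 57.5% v 52.8% | 0.5 |
| 0.05% (ptosis-like) | 5% | 5.0% v 0.05% | 2.0 | 5.4% v 0.4% | 1.8 |

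The contrast falls in every row, but by very different amounts: slightly for the ptosis-like event and by about two thirds at 8% background.

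**The case against.** **The plan already has summaries aimed at drug effects.** There is a concurrent placebo group, an overview row for investigator-related events, a summary of possible distant spread of toxin, and tables by maximum severity. This stands in part. Of the six events named in Protocol 2.2, however, only eyelid ptosis is in SAP Table B-1. The related-event summary is one readable overview row and depends on case-by-case attribution. The severity tables use the same open window, and background adds variance in both arms whether or not placebo is concurrent.

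**A long window is legitimate.** The protocol calls this a first-in-human study of the formulation, its timing statement describes BOTOX, and reactions may last months. This stands as a reason to keep the full-study tables, and the definition is not an error. The clause on several months concerns duration, so a filter on onset still counts an early event that persists.

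**Nothing readable proves an omission.** This stands. An onset-based table could lie in the redacted text. Interim timing is also redacted, so the 270-day percentages are not shown to be those behind the dose recommendation.

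**Stronger readings that the documents do not support**
- A reader might infer that background events are bound to overwhelm the drug signal. The documents give no background rates. At 1% per 30 days, only about half of the active-arm count at Day 270 is background (8.6/17.8 = 48%).
- A reader might suppose that placebo subjects leaving early would hide a drug effect. Less time at risk on placebo would lower its count and enlarge the apparent excess.
- A reader might reach for events per unit of subject-time. That summary suits a roughly constant hazard and fits poorly when risk is concentrated in the first days.

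**Conclusion.** The point holds as a cheap improvement to the reporting plan. After one injection the treatment-emergent window is open-ended, the protocol expects reactions early, and no readable table separates early from late onset. For complaints with appreciable background, the full-study percentage can be a markedly weaker display of an early effect: on the assumptions above, the contrast keeps about 57% of its 30-day value at 1% background (1.48/2.59), 37% at 5% (0.67/1.82) and 32% at 8% (0.49/1.53). For a ptosis-like event it keeps about 90% (1.81/2.02).

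These sizes depend on assumed rates, on a constant background, and on all of the drug excess falling within 30 days. That headache, nasopharyngitis and nausea belong among the higher-background complaints is a judgement; the documents give no rates for them. No planned test fails, since safety is descriptive.

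**What to change.** 1. Keep the 270-day treatment-emergent tables as planned.
2. In SAP 10.2.2 and 10.2.3, check whether the redacted text already has a summary by time of onset. If not, add the same overview and the same system organ class and preferred term tables, by treatment group, restricted to treatment-emergent events with onset in a prespecified early window. Thirty days after injection would serve. It is a convenient anchor, since Protocol 6.1 uses it as a minimum collection period and not as a risk window.
3. Include these tables in the safety package for each interim analysis (SAP 12.0).

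The cost is SAP wording and a date filter on existing table programs. No new data are needed, and type I error is unaffected because the tables are descriptive. The downside is a few more tables to produce and read.

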7.6 Interim Analyses

An interim analysis is planned to occur [REDACTED]

[REDACTED] If a dose recommendation cannot be made at this point, then a second interim analysis will be performed, [REDACTED]

The primary and secondary efficacy analyses will be performed for each interim analysis, as well as summaries of all safety variables.

[figure not shown]
[figure not shown]
The SAP will describe the planned interim analyses in detail. No separate SAP will be prepared for the interim analyses.

7.7 Overall Type I Error Control

Analyses will be conducted using a gated hierarchical testing procedure to preserve a familywise Type I error rate of $\alpha=0.05$ for each OnabotA X group.

7.8 Sample Size Determination

The sample size was chosen empirically. The primary efficacy parameter is the proportion of subjects with a ≥ 1 -grade improvement from baseline according to investigator-rated AGLSS at maximum contraction at Day 30. Based on previous BOTOX studies, the responder rate of ≥ 1 -grade improvement from baseline on the GL severity scale  Assuming  responder rate for OnabotA X and placebo, respectively, at least 28 OnabotA X and 14 placebo subjects will be required to detect the above intervention difference with a power of 90% or greater at the 2 sided 5% significance level for the primary endpoint.

8 ETHICS

8.1 Independent Ethics Committee/Institutional Review Board (IEC/IRB)

The protocol, informed consent form(s), recruitment materials, and all subject materials will be submitted to the IEC/IRB for review and approval. Approval of both the protocol and the informed consent form(s) must be obtained before any subject is enrolled. Any amendment to the protocol will require review and approval by the IEC/IRB before the changes are implemented to the study. In addition, all changes to the consent form(s) will be IEC/IRB approved.

8.2 Ethical Conduct of the Study

The study will be conducted in accordance with the protocol, Operations Manual, International Council for Harmonisation (ICH) guidelines, applicable regulations, and guidelines governing clinical study conduct and the ethical principles that have their origin in the Declaration of Helsinki. Responsibilities of the investigator are specified in [Appendix B](#).

In the event a significant disaster/crisis (e.g., epidemic/pandemic, natural disaster, conflict/combat) occurs leading to difficulties in performing protocol-specified procedures, AbbVie may engage with study site personnel in efforts to ensure the safety of subjects, maintain protocol compliance, and minimize risks to the integrity of the study while trying to best manage subject continuity of care. This may include alternative methods for assessments (e.g., phone contacts or virtual site visits), alternative locations for data collection (e.g., use of a local lab instead of a central lab) and shipping investigational product and/or supplies direct to subjects to ensure continuity of treatment where allowed. In all cases, these alternative measures must be allowed by local regulations and permitted by IRB/IEC. Investigators should notify AbbVie if any urgent safety measures are taken to protect the subjects against any immediate hazard.

8.3 Subject Confidentiality

To protect subjects' confidentiality, all subjects and their associated samples will be assigned numerical study identifiers or "codes." No identifiable information will be provided to AbbVie.

9 SOURCE DOCUMENTS AND CASE REPORT FORM COMPLETION

The investigator is responsible for ensuring the accuracy, completeness, legibility, and timeliness of the data reported. All source documents should be attributable, legible, contemporaneous, original, accurate, and complete to ensure accurate interpretation of data. Clinical site monitoring is conducted to ensure that the rights and well-being of human subjects are protected, that the reported trial data are accurate, complete, and verifiable, and that the conduct of the trial is in compliance with the currently approved protocol, ICH GCP, and applicable local regulatory requirement(s). During the COVID-19 pandemic, remote data review/verification may be employed if allowed by the local regulatory authority, IRB/IEC, and the study site.

10 DATA QUALITY ASSURANCE

AbbVie will ensure that the clinical trial is conducted with a quality management system that will define quality tolerance limits in order to ensure human subject protection and reliability of study results. Data will be generated, documented, and reported in compliance with the protocol, ICH GCP, and applicable regulatory requirements.

11 COMPLETION OF THE STUDY

The end-of-study is defined as the date of the last subject's last visit.

APPENDIX A. STUDY-SPECIFIC ABBREVIATIONS AND TERMS

Abbreviation	Definition
AE	adverse event
AGLSS	Allergan Glabellar Line Severity Scale
CMH	Cochran-Mantel-Haenszel
COVID-19	Coronavirus Disease – 2019
CRF	case report form
CS	clinically significant
DHEA	dehydroepiandrosterone
DMC	data monitoring committee
ECG	electrocardiogram
eCRF	electronic case report form
EDC	electronic data capture
ELISA	enzyme-linked immunosorbent assay
ePRO	electronic patient-reported outcome device
[REDACTED]	[REDACTED]
GCP	Good clinical practice
GL	glabellar lines
[REDACTED]	[REDACTED]
[REDACTED]	[REDACTED]
ICF	informed consent form
ICH	International Council for Harmonisation of Technical Requirements for Pharmaceuticals for Human Use
IDR	Independent Drug Reconstitutor
IEC	Independent ethics committee
IM	intramuscular
IMP	Investigational medicinal product
IRB	Institutional review board
IRT	Interactive response technology
[REDACTED]	[REDACTED]

Abbreviation	Definition
ITT	intent-to-treat
IUD	intrauterine device
MCMC	Markov chain Monte Carlo
MedDRA	Medical Dictionary for Regulatory Activities
MI	multiple imputation
N/A	not applicable
NCS	not clinically significant
[REDACTED]	[REDACTED]
OnabotA X	onabotulinumtoxinA X
PCR	polymerase chain reaction
PDSOT	possible distant spread of toxin
PRO	patient-reported outcomes
PT	preferred term
QT	time from the start of the Q wave to the end of the T wave
QTc	QT interval corrected for heart rate
QTcF	QT interval corrected for heart rate using Fridericia's formula
SAE	Serious adverse event
SAP	Statistical analysis plan
SAR	Serious adverse reactions
SARS-CoV-2	Severe acute respiratory syndrome coronavirus 2
SOC	system organ class
SUSAR	Suspected unexpected serious adverse reactions
TCA	trichloroacetic acid
U	units
VDS	verbal descriptor scale
WOCBP	woman of child-bearing potential

APPENDIX D. ACTIVITY SCHEDULE

The following table shows the required activities across the study. The individual activities are described in detail in the **Operations Manual**. Allowed modifications due to COVID-19 are detailed in the Operations Manual ([Appendix F](#)) in Section 2 and Section 3.

APPENDIX E. PROTOCOL SUMMARY OF CHANGES

Previous Protocol Versions

Protocol	Date
Version 2.0	07 September 2021
Version 1.0	14 June 2021

Version 3.0

The purpose of the version update to 3.0 is to change the number of estimated sites from approximately 15 to 18.

Version 2.0

[REDACTED]

Additional edits were made, as follows:

[REDACTED]

Added the following eligibility criterion to Section 5.1 Eligibility Criteria: "If the subject has received a

[REDACTED]

[REDACTED]

[REDACTED]

[REDACTED]

[REDACTED]

1.0 Introduction

This Statistical Analysis Plan (SAP) describes the statistical analyses for OnabotA X Study 2042-201-008 Glabellar Lines: OnabotulinumtoxinA X in the Treatment of Moderate to Severe Glabellar Lines.

Study 2042-201-008 examines the safety and efficacy of OnabotA X in subjects with moderate to severe glabellar lines.

The SAP will not be updated in case of administrative changes or amendments to the protocol unless the changes impact the analysis.

Unless noted otherwise, all analyses will be performed using SAS Version 9.4 (SAS Institute Inc., Cary, NC 27513) or later under the Linux operating system.

2.0 Study Design and Objectives

2.1 Objectives, Hypotheses and Estimands

The primary objectives of the study are to compare the efficacy of OnabotA X and placebo and to evaluate the safety of OnabotA X in subjects with moderate to severe GL.

The null and alternate hypotheses are the following:

$H_0: P_T = P_P$ (The treatment response probability between each OnabotA X treatment group and the placebo group is equal)

$H_A: P_T \neq P_P$ (The treatment response probability between each OnabotA X treatment group and the placebo group is not equal)

Estimand attributes of the primary efficacy endpoint are detailed in Table 1 (see Section 9.3.2). In addition, the attribute of treatment is a single dose of active treatment or placebo.

Differences in proportion of subjects who would achieve ≥ 1 -grade improvement from baseline on the investigator-rated AGLSS at maximum contraction at Day 30 had they not

missed AGLSS assessments, for each active treatment group (OnabotA X [REDACTED] [REDACTED]) in comparison with placebo in the ITT population.

Any missing assessments will be assumed to be missing at random and imputed using multiple imputation. Statistical significance of the difference will be tested using Cochran-Mantel-Haenszel (CMH) test stratified by baseline investigator-rated AGLSS at maximum contraction.

[figure not shown]
[REDACTED]
[REDACTED]
[REDACTED]
[REDACTED]
[REDACTED]

The clinical hypothesis is that OnabotA X has an acceptable safety profile when administered to the corrugator and procerus muscles in subjects with moderate to severe GL.

No estimand is defined for the safety evaluations.

